**Figure 1. Study Design Schematic**

### 4.3 Sample Size

Approximately 160 subjects will be randomized to the four treatment groups in a ratio of 1:1:1:1. The sample size for this study is based on the percent change in EASI from baseline at Week 16. Assuming a percent change in EASI from baseline at Week 16 of 35, 45, 60, and 70 in the placebo, 7.5 mg, 15 mg, and 30 mg arms with a standard deviation 40 and a maximum efficacy of 80, a sample size of 40 subjects per treatment group is sufficient to test for the presence of a dose response signal, to select the best dose response model for the observed data out of a pre-specified set of candidate models, and to estimate target doses of interest (e.g., the minimum effective dose, MED) via modeling

using the MCP-Mod (Multiple comparison procedure and modeling) approach. This approach provides 99% average power to detect a dose effect at the 5% level of significance (one-sided) with the linear,  $E_{\max}$ , exponential, logistic and  $\text{sig}E_{\max}$  models pre-specified as likely candidates to characterize the dose-response for upadacitinib for the percent change in EASI.

A sample of size 40 per group provides 97% power to detect a significant difference between 30 mg QD and placebo, and 78% power to detect a significant difference between 15 mg QD and placebo at the two-sided level of significance of 5.0%.

#### **4.4 Interim Analysis**

The analysis of safety and efficacy data for the first double blind period will be conducted after all subjects have either completed Period 1 or discontinued from the study. This efficacy analysis is the only and final analysis of Period 1, thus no adjustment of alpha-level is needed. In addition, there will be an interim analysis after all subjects have either reached Week 32 or discontinued from the study.

An external Data Monitoring Committee (DMC) comprised of persons independent of AbbVie and with relevant expertise in their field will review unblinded safety data from the ongoing study. If necessary the DMC will also be given access to efficacy data upon request. A DMC charter was prepared to describe the roles and responsibilities of the DMC members, frequency of data reviews, and relevant safety data to be assessed.

Communications from the DMC to the Study Teams will not contain information that could potentially unblind the team to subject treatment assignments.

### **5.0 Analysis Populations**

#### **5.1 Analysis Populations**

##### **Intent-to-Treat (ITT) Population**

An ITT population will be defined for each period and be used for the efficacy analyses.

---

- The ITT Population in Period 1 (ITT\_1) is defined as all subjects who are randomized at Day 1.
- The ITT Population in Period 2 (ITT\_2) is defined as all subjects who are re-randomized at the entry of Period 2.

For efficacy analyses, subjects included in the ITT populations will be analyzed as randomized. If a subject is randomized or re-randomized in the wrong strata, the subject will be analyzed according to the actual strata that subject belongs to.

### **Safety Population**

A Safety population will be defined for each period and be used for safety analyses.

- The Safety Population in Period 1 (Safety\_1) is defined as all subjects who are randomized and receive at least one dose of study drug in Period 1.
- The Safety Population in Period 2 (Safety\_2) is defined as all subjects who are re-randomized at the entry of Period 2 and receive at least one dose of study drug in Period 2.

For the Safety populations, subjects are assigned to a treatment group based on the "as treated" treatment group. In the case where the subject received more than one treatment, the "as treated" is determined by the dosage that a patient received the most during a period.

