5.2.3.4 Rescue Therapy

For subjects re-randomized to placebo, ABT-494 7.5 mg QD or ABT-494 15 mg QD in Period 2, blinded rescue therapy with ABT-494 30 mg QD will be provided after the first instance of a < EASI 50 response starting at the Week 20 visit (4 weeks after re-randomization into Period 2). These subjects will continue on ABT-494 30 mg QD for the remainder of the study.

During Period 2, concomitant class III – IV, medium potency topical corticosteroid treatment will be permitted at the Week 24 visit and thereafter in subjects after a second instance of < EASI 50 response in any two Period 2 study visits beginning from Week 20. For subjects who receive topical corticosteroid rescue therapy, an additional visit will be

required 4 weeks after receiving topical corticosteroid rescue therapy. Discontinuation from study drug will be mandatory for subjects with < EASI 50 response compared with their Baseline EASI score 4 weeks following rescue with topical corticosteroids or at any visit thereafter.

Topical treatment allowed is limited to up to twice daily triamcinolone acetonide 0.1% cream or up to once daily mometasone furoate 0.1% cream. Use of a topical corticosteroid treatment should be recorded on the appropriate concomitant medication eCRF.

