- t. HIV testing will be performed at Screening. The Investigator must discuss any local reporting requirements to local health agencies with the subject. The site will report confirmed positive results to their health agency per local regulations, if necessary. If the result is confirmed as positive, then the Investigator will discuss with the subject potential implications to the subject's health and next steps. If a subject has a confirmed positive result, the Investigator must discuss with the subject the potential implications to the subject's health and subject should receive or be referred for clinical care promptly. This testing is to be done at the central lab. A subject will not be eligible for study participation if test results indicate a positive HIV infection. AbbVie will not receive results from the testing and will not be made aware of any positive result.
- u. At Week 2 and Week 4 visits, PK samples should be collected prior to dosing and the subjects should take the study drug dose at the clinic after collecting the PK blood sample. However, if the subject normally takes the study drug dose at a time that is after the time of the scheduled study visit, the subject should follow the regular dosing schedule and the PK sample will be collected at any time during the visit.

Table 2. Study Activities (Continued)

- v. PK samples will be collected at any time during the visit. Subject should follow the regular dosing schedule.
- w. Samples only collected if subject provides written consent. Subjects should be in fasting condition (8 hours, except for water) prior to samples collection. For selected sites, these assessments (blood samples and skin biopsies collection) will be made mandatory as part of the main study.
- x. Visits are every 12 weeks from the Week 40 visit to the Week 88 visit (Wk 52, Wk 64, Wk 76, and Wk 88).
- y. A visit will be required 4 weeks after receiving topical rescue therapy. After this visit, patients will continue to follow the standard protocol visit schedule, as applicable from that date (Wk 32, Wk 40, Wk 52, Wk 64, Wk 76, and Wk 88).
- z. Study Drug Dispensing stops at the Week 76 visit.

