Note 1: Visit window is ± 3 days for Period 1 (Weeks 2, 4, 8, 12 and 16) and ± 5 days for Period 2 (Weeks 20, 24, 32, 40, 52, 64, 76 and 88) and a visit 4 weeks following topical rescue if applicable. Any of the procedures may be performed at the discretion of the investigator. Subjects who choose to discontinue study drug treatment, but continue to participate in the study, should complete a Premature Discontinuation Visit (PD Visit) as soon as possible, preferably within 2 weeks. Afterwards, subjects should follow the regular visit schedule and adhere to all study procedures except for dispensing study drug, PK sample collection, and blood and skin sample collection for exploratory research and validation studies. In addition, all future rescue and efficacy-driven discontinuation criteria no longer apply.

Note 2: Twice daily use of an additive-free, bland emollient is required for at least 7 days prior to Baseline and during the study.

Table 3. Study Activities – Optional and Mandatory Samples for Exploratory Research and Validation Studies

Activity	Screening D -30 to D -1	BL	Wk 2	Wk 4	Wk 8	Wk 12	Wk 16	Wk 20	Wk 24	Wk 32	Wk 40	Every 12 Weeks or PD ^a D365 – D617	4 Weeks Post Topical Rescue Visit	30- Day F/U Visit
Pharmacogenetic samples ^a		X												
Epigenetic samples ^a		X	X	X			X	X						
Transcriptomic and epigenetic samples ^a		X	X	X			X	X						
Plasma samples for analyses including, but not limited to, proteomic and targeted protein investigations ^a		X	X	X			X	X						
Serum samples for analyses including, but not limited to, proteomic and targeted protein investigations ^a		X	X	X			X	X						
Sample for PBMC assays ^a		X		X			X							
Skin Biopsies for analyses including, but not limited to, epigenetics, transcriptomics, proteomics, immunohistochemistry ^{a,b} and targeted investigations		X		X			X							

BL = Baseline Visit; D = Day; F/U = Follow-Up; PBMC = Peripheral Blood Mononuclear Cell; PD = Premature Discontinuation; Wk = Week

- Based on the value of the different technologies, samples may also be used to assess other biomarker signatures, including but not limited to metabolomics, lipidomics, and other approaches. Samples may be used for assay of study drugs if needed.

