Starting at the Week 20 visit (4 weeks after re-randomization into Period 2), rescue therapy with upadacitinib 30 mg QD will be provided to subjects who have a first instance of an EASI score improvement of less than 50% (i.e., < EASI 50 response), when compared against the Baseline. These subjects will continue on upadacitinib 30 mg QD for the remainder of the study.

[figure not shown]
During Period 2, concomitant class III – IV, medium potency topical corticosteroid treatment will be permitted at the Week 24 visit and thereafter in subjects after a second instance of < EASI 50 response in any two Period 2 study visits beginning from Week 20 (see Protocol Section 5.2.3.4 for permitted treatments). For subjects who receive topical corticosteroid rescue therapy, a visit will be required 4 weeks after receiving the rescue therapy. Discontinuation from study drug will be mandatory for subjects with < EASI 50 response compared with their baseline EASI score 4 weeks following rescue with topical corticosteroids or at any visit thereafter.

In order to minimize missing data for efficacy and safety assessments, subjects who prematurely discontinue study drug should continue to be followed for all regularly scheduled visits, unless they have decided to discontinue the study participation entirely (withdrawal of informed consent).

A schematic of the overall study design is shown in [Figure 1](#).

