**Table 1. Notations for Treatment Groups**

Population	Treatment Code	Definition
ITT_1 and Safety 1	UPA 7.5 MG	Upadacitinib 7.5 mg.
	UPA 15 MG	Upadacitinib 15 mg.
	UPA 30 MG	Upadacitinib 30 mg.
	PBO	Placebo
ITT_2 and Safety 2	UPA 7.5 MG/UPA 7.5 MG	Upadacitinib 7.5 mg in Period 1 and upadacitinib 7.5 mg in Period 2
	UPA 7.5 MG/PBO	Upadacitinib 7.5 mg in Period 1 and placebo in Period 2
	UPA 15 MG/UPA 15 MG	Upadacitinib 15 mg in Period 1 and upadacitinib 15 mg in Period 2
	UPA 15 MG/PBO	Upadacitinib 15 mg in Period 1 and placebo in Period 2
	UPA 30 MG/UPA 30 MG	Upadacitinib 30 mg in Period 1 and upadacitinib 30 mg in Period 2
	UPA 30 MG/PBO	Upadacitinib 30 mg in Period 1 and placebo in Period 2
	PBO/UPA 30 MG	Placebo in Period 1 and upadacitinib 30 mg in Period 2
	PBO/PBO	Placebo in Period 1 and placebo in Period 2

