### **Period 2:**

- Date of last dose of study drug in Period 2– Date of first dose of study drug in Period 2 + 1.
- For interim analysis at Week 32, minimum of the above and (cutoff date – Date of first dose of study drug in Period 2 + 1).

Additional summaries of upadacitinib exposures by dose level will also be performed including exposure to each dose level across periods.

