### **11.2.1 Treatment-Emergent Adverse Events**

A treatment-emergent Adverse Event (TEAE) is defined as an adverse event with an onset or worsening date that is on or after the first dose of study drug, and no more than 30 days after the last dose of study drug.

AEs where the onset date is the same as the study drug start date are assumed to be treatment-emergent. If an incomplete onset date was collected for an adverse event, the event will be assumed to be treatment-emergent unless there is other evidence that confirms that the event was not treatment-emergent (e.g., the event end date was prior to the study drug start date).

TEAEs for the safety population in each period are defined as an event with a start date on or after the date of first study drug dose in each period and up to 30 days after the last dose of study drug in the analysis period, or prior to the date of first dose in the subsequent period for subjects who entered in to the subsequent period.

Adverse event data will be coded using the Medical Dictionary for Drug Regulatory Activities (MedDRA) version 20.0 or most up to date version.

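### Period 2 adverse events and exposure are not split at rescue to 30 mg, so the most-received-dosage rule files mixed treatment time under one Safety_2 label

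*SAP*

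**What the plan says.** **Rescue.** Protocol 5.2.3.4 provides 30 mg rescue at the first response below EASI 50 from Week 20, for subjects re-randomised to placebo, 7.5 mg or 15 mg. It is permanent: "These subjects will continue on ABT-494 30 mg QD for the remainder of the study". SAP 4.2 agrees ("These subjects will continue on upadacitinib 30 mg QD for the remainder of the study"), though it does not restrict rescue by arm. On the protocol's wording, six of the eight Period 2 arms can be rescued; 30/30 and PBO/30 cannot.

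**Safety windows.** In SAP 11.2.1 a Period 2 event counts as treatment-emergent from the first Period 2 dose "up to 30 days after the last dose of study drug in the analysis period". SAP 9.1 measures Period 2 exposure from first to last Period 2 dose, and SAP 11.2.1.7 uses that exposure as the denominator for rates per 100 patient-years. None of these stops at rescue.

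**Windows that do stop.** SAP 9.2 ends Period 2 compliance the day before the first rescue dose. SAP 10.1.5 drops efficacy assessments made after that dose.

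**Grouping.** For a subject who took more than one treatment in a period, SAP 5.1 says the as-treated group "is determined by the dosage that a patient received the most during a period". SAP Table 1 lists eight codes for Safety_2, of the form "Upadacitinib 7.5 mg in Period 1 and upadacitinib 7.5 mg in Period 2". None denotes 7.5 mg or 15 mg in Period 1 followed by 30 mg in Period 2.

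**Supplementary summaries.** SAP 11.2 adds adverse-event summaries for time on upadacitinib monotherapy at each dose level across both periods. SAP 9.1 adds the matching exposure: "Additional summaries of upadacitinib exposures by dose level will also be performed including exposure to each dose level across periods".

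**The concern.** Protocol 8.1.6.1 bases safety analysis on the treatment actually received, and Protocol 5.6.1 gives Period 2 the job of showing longer-term safety. A most-received-dosage rule suits occasional dispensing errors. Here it meets a planned, permanent change of treatment whose date the SAP already needs for compliance and efficacy. Because the safety windows do not stop at that date, every event and day on one side of rescue is reported under a treatment the subject was not taking. A reader of a Safety_2 table could then take events on placebo for events on 30 mg, or the reverse. The label also depends on how long the subject has been dosed by the time of the analysis.

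**Working it through.** The plan gives no figure of its own on this point, so there is none to reproduce. The check applies the SAP 5.1 rule to the nominal visit schedule.

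**Inputs**
- Period 2 visits at Weeks 20, 24, 32, 40, 52, 64, 76 and 88, with the last dose the day before Week 88 (Protocol 5.1).
- Week 88 is nominal Period 2 Day 505 (SAP Table 7), so there are 504 dosing days, or 504/365.25 = 1.38 patient-years.
- Week 76 is the latest visit at which rescue drug can be handed out: "Study Drug Dispensing stops at the Week 76 visit" (Protocol Table 2, footnote z).
- Assumption: daily dosing to Week 88.

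**Formulas.** For rescue at Week r, days before rescue = 7 × (r − 16), and days on 30 mg = 504 − 7 × (r − 16). The label follows the larger count. The misplaced time is the smaller count, divided by 504 for the share and by 365.25 for patient-years.

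| Rescue week | Days before | Days on 30 mg | Label under SAP 5.1 | Misplaced share | Misplaced patient-years |
|---|---|---|---|---|---|
| 20 | 28 | 476 | 30 mg | 5.6% | 0.08 |
| 24 | 56 | 448 | 30 mg | 11.1% | 0.15 |
| 32 | 112 | 392 | 30 mg | 22.2% | 0.31 |
| 40 | 168 | 336 | 30 mg | 33.3% | 0.46 |
| 52 | 252 | 252 | tie, no rule | 50% | 0.69 |
| 64 | 336 | 168 | re-randomised arm | 33.3% | 0.46 |
| 76 | 420 | 84 | re-randomised arm | 16.7% | 0.23 |

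At Week 52 the ±5 day visit window (Protocol Table 2, Note 1) decides the label.

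**Early stopping changes the counts.** Suppose a subject is rescued at Week 40, is below EASI 50 again at Week 52, starts topical steroid, and is still below EASI 50 at the extra visit four weeks later. Study drug stops at Week 56 (Protocol 5.2.3.4). The counts are 168 days before and 7 × (56 − 40) = 112 days on 30 mg, so the label is the re-randomised arm rather than 30 mg, and the misplaced share is 112/280 = 40%.

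**Codes.** When the label becomes 30 mg:
- subjects from 7.5/7.5, 7.5/PBO, 15/15 and 15/PBO need a 7.5/30 or 15/30 code, and Table 1 has neither;
- subjects from PBO/PBO and 30/PBO join the randomised PBO/30 and 30/30 columns and bring their placebo time with them.

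**Week 32 interim.** For a subject with exactly 112 Period 2 days:
- rescue at Week 20 gives 28 v 84 days (30 mg);
- rescue at Week 24 gives 56 v 56 (tie);
- rescue at Week 32 gives 112 v 0 (re-randomised arm), which turns to 30 mg once dosing passes Week 48.

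The same subject can therefore sit in different columns at the interim and final analyses.

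**Column level, as an illustration only.** The documents give no rescue rate. Assume equal arms, no dropout and a fraction f rescued at one visit.
- PBO/PBO subjects merged into PBO/30: placebo share of the column = f × (r − 16) / ((1 + f) × 72). For f = 10%, 25%, 50% this is 0.5%, 1.1%, 1.9% at Week 20 and 3.0%, 6.7%, 11.1% at Week 40.
- Rescue at Week 64, where subjects stay in their column: 30 mg share = f × 24/72, or 3.3%, 8.3%, 16.7%.

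**The case against.** The strongest reply is that the SAP has a rule and has already covered the main safety question. SAP 5.1 speaks of any subject who took more than one treatment, which plainly includes rescued subjects, and an as-treated rule of this kind is one way to meet the protocol. The dose-level summaries in SAP 11.2 and 9.1 separate 7.5, 15 and 30 mg time, including time after rescue. Individual cases appear in the listings (SAP 11.2.3, 11.3.2.3, 11.4.2), and an external committee reviews unblinded safety data (SAP 4.4). With at most about 160/8 = 20 subjects per Period 2 arm, a split makes small groups smaller and does not restore a randomised comparison.

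Most of this stands, and it is why the weight is modest. It leaves three things uncovered. No summary is named for placebo time before rescue. The arm-level Safety_2 adverse-event tables remain mixed. The dose-level provision covers adverse events and exposure only, so the Period 2 laboratory shift, Grade 3 or above and vital-sign summaries are not separated.

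Two stronger readings are tempting. A reader might infer that SAP 5.1 says nothing on how to group rescued subjects; its sentence on subjects with more than one treatment is such a rule, although it lacks a tie-break and produces groups that Table 1 does not list. A reader might also infer from Table 1's eight codes that rescued subjects stay in their re-randomised column, which would put up to 476 of 504 days (94%) of 30 mg time under placebo, 7.5 mg or 15 mg. Using the codes unchanged would indeed leave more 30 mg time under those labels. But Table 1 is a list of notations shared with ITT_2; no sentence says rescued subjects stay put, and SAP 5.1 says otherwise.

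**Conclusion.** The point holds at modest severity. The rule as written, applied to windows that are not cut at rescue, misattributes 6% to 33% of a rescued subject's Period 2 time and the events in it, and 50% at the Week 52 tie. These figures rest on nominal visits and dosing to Week 88. With early stopping the share differs, but under a most-received rule with two treatments it cannot exceed one half. How much of a whole column is affected cannot be fixed without a rescue rate.

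The effect is confined to descriptive Period 2 safety tables. Between-group safety comparisons are planned for Period 1 only (SAP 11.1, 11.3.2.1, 11.4.2), so no Period 2 safety test, Period 1 result or primary analysis is affected.

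**What to change.** In SAP 5.1, 9.1 and 11:
- Split Safety_2 adverse events, laboratory values, vital signs and patient-years at the first 30 mg rescue dose. Report earlier time under the re-randomised arm. Report later time under a rescued-to-30 mg group added to Table 1, pooled and by re-randomised arm where numbers allow.
- Limit the most-received-dosage rule to dispensing errors, but only together with the split. Made alone, that edit would leave rescued subjects' 30 mg time under their re-randomised label and increase the mixing.
- State a rule for events starting on the day of the first rescue dose. The SAP is not consistent on the parallel case: SAP 6.0 assigns events on the first Period 2 dosing day to Period 1, while SAP 11.2.1 assigns them to Period 2.
- State in SAP 11.2.1.7 that events and patient-years use the same split.
- Label the columns descriptive.

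The cost is SAP wording, extra rows in Table 1 and a time split in the safety datasets; the rescue date is already needed for SAP 9.2 and 10.1.5. The drawbacks are shorter follow-up per column, small rescued groups made up only of subjects who lost or lacked response, and pre-rescue time that comes increasingly from continuing responders.

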**Table 1. Notations for Treatment Groups**

Population	Treatment Code	Definition
ITT_1 and Safety 1	UPA 7.5 MG	Upadacitinib 7.5 mg.
	UPA 15 MG	Upadacitinib 15 mg.
	UPA 30 MG	Upadacitinib 30 mg.
	PBO	Placebo
ITT_2 and Safety 2	UPA 7.5 MG/UPA 7.5 MG	Upadacitinib 7.5 mg in Period 1 and upadacitinib 7.5 mg in Period 2
	UPA 7.5 MG/PBO	Upadacitinib 7.5 mg in Period 1 and placebo in Period 2
	UPA 15 MG/UPA 15 MG	Upadacitinib 15 mg in Period 1 and upadacitinib 15 mg in Period 2
	UPA 15 MG/PBO	Upadacitinib 15 mg in Period 1 and placebo in Period 2
	UPA 30 MG/UPA 30 MG	Upadacitinib 30 mg in Period 1 and upadacitinib 30 mg in Period 2
	UPA 30 MG/PBO	Upadacitinib 30 mg in Period 1 and placebo in Period 2
	PBO/UPA 30 MG	Placebo in Period 1 and upadacitinib 30 mg in Period 2
	PBO/PBO	Placebo in Period 1 and placebo in Period 2

## 5.2 Variables Used for Stratification of Randomization

For Period 1, the randomization will be stratified by geographic region (US/PR/Canada, EU/AUS, and Japan); for Period 2, the re-randomization will be stratified by geographic region and EASI 75 response at Week 16.

## 6.0 Analysis Windows

### Definition of Baseline

Baseline refers to the last non-missing observation prior to the first dose of study drug. For randomized but not treated subjects, the baseline value will be the last non-missing measurement recorded prior to the randomization.

